5.1.1 Treatment After End of Study

For subjects receiving upadacitinib, as the subject nears the end of the study (Week 260 in Period 2), the investigator will discuss the appropriate subsequent treatment with the subject. If the subject and investigator determine continued therapy with upadacitinib remains the best course of treatment, AbbVie will work with the investigator to evaluate a path for continued treatment in accordance with local regulation until upadacitinib is commercially available and/or the subject can access upadacitinib locally (refer to Appendix I for further details).

All subjects randomized to the adalimumab treatment arm will have the opportunity to continue with adalimumab treatment through the end of Period 2 (Week 260). Following completion of the Week 260 visit, subjects randomized to adalimumab will complete the study by the 70-day follow-up phone call.

5.2 Selection of Study Population

[figure not shown]
It is anticipated that approximately 1640 subjects with active PsA with inadequate response to at least one non-biologic DMARD will be randomized at approximately 350 study centers, globally.

A subject may be enrolled in this study provided that he/she has met all of the inclusion criteria specified in Section 5.2.1 and none of the exclusion criteria specified in Section 5.2.2 of this protocol.

5.2.1 Inclusion Criteria

- 1. Adult male or female, at least \geq 18 years old at Screening.
- 2. Clinical diagnosis of PsA with symptom onset at least 6 months prior to the Screening Visit and fulfillment of the Classification Criteria for PsA (CASPAR) criteria.
- Subject has active disease at Baseline defined as ≥ 3 tender joints (based on 68 joint counts) and ≥ 3 swollen joints (based on 66 joint counts) at Screening and Baseline Visits.
- 4. Presence of either at Screening:
 - ≥ 1 erosion on x-ray as determined by central imaging review or;
 - hs-CRP > laboratory defined upper limit of normal (ULN).
- 5. Diagnosis of active plaque psoriasis or documented history of plaque psoriasis.
- 6. Subject has had an inadequate response (lack of efficacy after a minimum 12 week duration of therapy) to previous or current treatment with at least 1 non-biologic DMARD at maximally tolerated dose or up to dose defined in Inclusion Criterion 7 [(inadequate response to MTX is defined as ≥ 15 to ≤ 25 mg/week; or ≥ 10 mg/week in subjects who are intolerant of MTX at doses ≥ 12.5 mg/week after complete titration; for subjects in China, South Korea, Malaysia, Singapore, Hong Kong (China), Taiwan, and Japan inadequate response to MTX is defined as ≥ 7.5 mg/week), SSZ, LEF, cyclosporine, apremilast, bucillamine or iguratimod], or subject has an intolerance to or contraindication for DMARDs as defined by the investigator.
- 7. Subject who is on current treatment with concomitant non-biologic DMARDs at study entry must be on ≤ 2 non-biologic DMARDs (except the combination of

[figure not shown]
MTX and leflunomide) at the following doses: MTX (\leq 25 mg/week), SSZ (\leq 3000 mg/day), leflunomide (LEF) (\leq 20 mg/day), apremilast (\leq 60 mg/day), HCQ (\leq 400 mg/day), bucillamine (\leq 300 mg/day) and iguratimod (\leq 50 mg/day) for \geq 12 weeks and at stable dose for \geq 4 weeks prior to the Baseline Visit. No other DMARDs are permitted during the study. Use of MTX in combination with LEF is prohibited. Subjects who need to discontinue DMARDs prior to the Baseline Visit to comply with this inclusion criterion must follow the procedure specified below or at least five times the mean terminal elimination half-life of a drug:

- \geq 8 weeks for LEF if no elimination procedure was followed, or adhere to an elimination procedure (i.e., 11 days with cholestyramine, or 30 days washout with activated charcoal or as per local label);
- \geq 4 weeks for all others.
- 8. Stable doses of non-steroidal anti-inflammatory drugs (NSAIDs), acetaminophen/paracetamol, low-potency opiates (tramadol or combination of acetaminophen and codeine or hydrocodone), oral corticosteroids (equivalent to prednisone ≤ 10 mg/day), or inhaled corticosteroids for stable medical conditions are allowed, but must have been at a stable dose for ≥ 1 week prior to the Baseline Visit.
- 9. Subjects must have discontinued all opiates (except for tramadol, or combination of acetaminophen and codeine or hydrocodone) at least 1 week and oral traditional Chinese medicine for at least 4 weeks prior to the first dose of study drug (refer to Section 5.2.3.3 for prohibited medications).
- 10. Where mandated by local requirements only, treatment with at least one of the following background medications is required: non-biologic DMARDs, NSAIDs, acetaminophen, low potency opiates (tramadol or combination of acetaminophen codeine or hydrocodone), or oral corticosteroids at doses described in Inclusion Criteria 7 and 8.

- 11. Women of childbearing potential (refer to Section 5.2.4), must not have a positive serum pregnancy test at the Screening Visit and must have a negative urine pregnancy test at the Baseline Visit-prior to study drug dosing. Where mandated by local requirements a negative serum pregnancy test will be required.
 - Note: Subjects with a borderline serum pregnancy test at Screening must have a serum pregnancy test ≥ 3 days later to document continued lack of a positive result.
- 12. If female, subject must be postmenopausal OR permanently surgically sterile OR for women of childbearing potential practicing at least one protocol specified method of birth control (Section 5.2.4) that is effective from the Baseline visit through at least 150 days after the last dose of subcutaneous study drug, and 30 days after the last dose of oral study drug.
 - Additional local requirements may apply. Refer to Appendix H.
- 13. Subjects must voluntarily sign and date an informed consent, approved by an Independent Ethics Committee (IEC)/Institutional Review Board (IRB), prior to the initiation of any screening or study-specific procedures. For subjects in Japan only: if a subject is under 20 years of age, then the subject and their parent or legal guardian must voluntarily sign and date an informed consent.

Rationale for Inclusion Criteria

[figure not shown]
1 - 10	To select the appropriate subject population
11 – 12	The effect of upadacitinib on pregnancy and reproduction is unknown
13	In accordance with harmonized Good Clinical Practice (GCP)

5.2.2 Exclusion Criteria

[figure not shown]
A subject will not be eligible for study participation if he/she meets any of the following criteria:

- 1. Prior exposure to any biologic immunomodulation agents.
- 2. Prior exposure to any Janus Kinase (JAK) inhibitor (including but not limited to ruxolitinib, tofacitinib, baricitinib, and filgotinib).
- 3. Has been treated with any investigational drug within 30 days or five half-lives of the drug (whichever is longer) prior to the first dose of study drug or is currently enrolled in another interventional clinical study.
- 4. Current treatment with > 2 non-biologic DMARDs or use of DMARDs other than MTX, SSZ, LEF, apremilast, HCQ, bucillamine or iguratimod or use of MTX in combination with LEF at Baseline.
- 5. Current or past history of infection including:
 - History of recurrent or disseminated (even a single episode) herpes zoster;
 - History of disseminated (even a single episode) herpes simplex;
 - History of known invasive infection (e.g., listeriosis and histoplasmosis);
 - Active human immunodeficiency virus (HIV) or immunodeficiency syndrome. Active HIV is defined as confirmed positive anti-HIV antibody (HIV Ab) test;
 - Subject has active TB or meets TB exclusionary parameters (refer to Section 5.3.1.1 for specific requirements for TB testing);
 - For subjects in Japan only: Positive result of beta-D-glucan or two consecutive indeterminate results of beta-D-glucan (screening for pneumocystis jiroveci infection).
 - Active infection(s) requiring treatment with parenteral anti-infectives within 30 days, or oral anti-infectives within 14 days prior to the Baseline Visit.
 - Chronic recurring infection and/or active viral infection that based on the investigator's clinical assessment makes the subject an unsuitable candidate for the study;

• Active HBV or HCV defined as:

[figure not shown]
- o HBV: hepatitis B surface antigen (HBs Ag) positive (+) or detected sensitivity on the HBV deoxyribonucleic acid (DNA) polymerase chain reaction (PCR) qualitative test for hepatitis B core antibody (HBc Ab) positive (+) subjects (and for Hepatitis B surface antibody positive [+] subjects in China, Japan and South Korea, or where mandated by local requirements);
- HCV: HCV ribonucleic acid (RNA) detectable in any subject with anti-HCV antibody (HCV Ab).
- 6. Underlying medical diseases or problems including but not limited to the following:
 - History of any of the following cardiovascular conditions:
 - Moderate to severe congestive heart failure (New York Heart Association class III or IV);
 - Recent (within past 6 months) cerebrovascular accident, myocardial infarction, coronary stenting;
 - Uncontrolled hypertension as defined by a confirmed systolic blood pressure > 160 mmHg or diastolic blood pressure > 100 mmHg;
 - Subject has been a previous recipient of an organ transplant which requires continued immunosuppression;
 - History of gastrointestinal perforation (other than appendicitis or penetrating injury), diverticulitis, or significantly increased risk for GI perforation per investigator judgment;
 - Conditions that could interfere with drug absorption including but not limited to short bowel syndrome;
 - History of any malignancy except for successfully treated non-melanoma skin cancer (NMSC) or localized carcinoma in situ of the cervix;
 - History of demyelinating disease such as Multiple Sclerosis or neurologic symptoms suggestive of demyelinating disease (including myelitis);
 - History of clinically significant medical conditions or any other reason which in the opinion of the investigator would interfere with the subject's

participation in this study or would make the subject an unsuitable candidate to receive study drug or would put the subject at risk by participating in the protocol; or permanently wheelchair-bound or bedridden or very poor functional status which prevents the ability to perform self-care.

- 7. Use of the following concomitant psoriasis treatments within the specified timeframe:
 - Oral retinoids within 4 weeks of the Baseline visit;
 - Fumarates within 1 week of the Baseline Visit:
 - Psoralens and Ultraviolet A (PUVA) within 4 weeks of the Baseline visit;
 - Ultraviolet A (UVA) or Ultraviolet B (UVB); or Laser therapy within 2 weeks of the Baseline visit;
 - All topical psoriasis treatments, including medicated shampoos, within 2 weeks of the Baseline visit. The following exceptions are allowed:
 - Bland (without beta or alpha hydroxy acids, urea or salicylic acids)
 emollients
 - Low potency (Class VI or VII) topical corticosteroids on the palms, soles, face, inframammary area and groin only.
 - Topical anti-itch treatment with no expected effect on psoriatic skin lesions.
- 8. Systemic use of known strong cytochrome P450 (CYP) 3A inhibitors or strong CYP3A inducers from Screening through the last dose of the study drug (refer to Table 1 for examples of commonly used strong CYP3A inhibitors and inducers).
- 9. Receipt of any live vaccine within 4 weeks (8 weeks in Japan) prior to the Baseline Visit, or expected need of live vaccination during study participation including at least 4 weeks (8 weeks in Japan) after the last dose of oral study drug, and including at least 70 days after the last dose of subcutaneous study drug.
- 10. Subject has received oral or parenteral Traditional Chinese Medicines within 4 weeks prior to Baseline, has received opioid analgesics (except for tramadol or combination of acetaminophen and codeine or hydrocodone which are allowed)

- within 1 week prior to Baseline, or use of inhaled marijuana within 2 weeks prior to Baseline.
- 11. History of an allergic reaction or significant sensitivity to constituents of the study drugs (including adalimumab or its excipients) and/or other products in the same class.
- 12. History of fibromyalgia, any arthritis with onset prior to age 17 years or current diagnosis of inflammatory joint disease other than PsA (including, but not limited to rheumatoid arthritis, gout, overlap connective tissue diseases, scleroderma, polymyositis, dermatomyositis, systemic lupus erythematosus.) Prior history of reactive arthritis or axial spondyloarthritis including ankylosing spondylitis and non-radiographic axial spondyloarthritis is permitted if documentation of change in diagnosis to PsA or additional diagnosis of PsA is made. Prior history of fibromyalgia is permitted if documentation of change in diagnosis to PsA or documentation that the diagnosis of fibromyalgia was made incorrectly.
- 13. History of clinically significant (per Investigator's judgment) drug or alcohol abuse within the last 6 months preceding the Baseline Visit.
- 14. Female subject who is pregnant, breastfeeding or is considering becoming pregnant during the study within 150 days after the last dose of subcutaneous study drug, and within 30 days after the last dose of oral study drug.
- 15. Laboratory values meeting the following criteria within the Screening period:
 - Serum aspartate transaminase (AST) $> 2 \times ULN$;
 - Serum alanine transaminase (ALT) $> 2 \times ULN$;
 - Estimated glomerular filtration rate (GFR) by simplified 4-variable Modification of Diet in Renal Disease (MDRD) formula
 40 mL/min/1.73 m²;
 - Total white blood cell count (WBC) < 2,500/μL;
 - Absolute neutrophil count (ANC) $< 1,500/\mu L;$
 - Platelet count $< 100,000/\mu L$;
 - Absolute lymphocyte count < 800/μL;

- Hemoglobin < 10 g/dL.
- 16. Active skin disease other than psoriasis that would interfere with the assessment of psoriasis.
- 17. Subject with extra-articular manifestations of PsA (e.g., PsO, uveitis, or IBD) that are not clinically stable for at least 30 days prior to study entry.
- 18. Subject has had joint surgery at joints to be assessed within this study or has been treated with intra-articular, intramuscular, intravenous, trigger point or tender point, intra-bursa, or intra-tendon sheath corticosteroids in the preceding 8 weeks prior to the Baseline visit.
- 19. Consideration by the Investigator, for any reason, that the subject is an unsuitable candidate to receive upadacitinib or adalimumab or subject has any contraindication to adalimumab, according to the local label.

Rationale for Exclusion Criteria

1-4 To select the appropriate subject population 14 The impact of upadacitinib on pregnancies is unknown 5-13, 15-19 To ensure safety of the subjects throughout the study

5.2.3 Prior and Concomitant Therapy

Any medication or vaccine (including over-the-counter or prescription medicines, vitamins and/or herbal supplements including folic acid) that the subject is receiving within 28 days prior to Screening and/or receives during the study, must be recorded along with the reason for use, date(s) of administration including start and end dates, and dosage information including dose, route and frequency must be recorded in the eCRF.

In addition, for subject's \leq 30 years old with a reported malignancy AE, prior exposure to, or current use of antineoplastics, or other drugs which have a risk of malignancy as stated in their label and other relevant dosing information to estimate total exposure will be

[figure not shown]
collected in the source documents and appropriate eCRF pages. At the time of the reported malignancy AE, sites will be asked if any of the below prior and concomitant medication categories contributed to the event. Any medications in these categories used prior to the study will be captured on the appropriate eCRF. Information on the reason for use, date(s) of administration including start and end dates, highest maintained dose, dosage information including dose, route and frequency, and reason for stopping the medication will be collected in the source documents and appropriate eCRF pages.

Medication Categories:

- corticosteroids
- immunosuppressants
- biologic agents
- antineoplastics
- other

Vaccines

Vaccines recommended by local guidelines should be considered. If the investigator chooses to administer a vaccine, this should be completed before first dose of study drug with appropriate precautions and time interval. It is recommended that subjects be up to date for recommended inactivated, toxoid or biosynthetic vaccines, such as injectable flu vaccine, pneumococcal, and pertussis (Tdap). It is recommended that the live herpes zoster vaccine should be considered for administration at least 4 weeks (8 weeks in Japan) before first dose of study drug or administered at least 30 days after last dose of oral study drug, or at least 70 days after last dose of subcutaneous study drug. If the herpes zoster vaccine is to be administered, and there is no known history of primary varicella (chicken pox), pre-existing immunity to varicella should be confirmed with antibody testing at or prior to screening and prior to administration of the herpes zoster vaccine. If screening varicella antibody testing is negative the herpes zoster vaccine should not be administered. See Section 5.2.3.3 for a list of commonly used live vaccines.

The AbbVie Therapeutic Area Medical Director (TA MD) should be contacted if there are any questions regarding concomitant or prior therapy(ies).

[figure not shown]
5.2.3.1 Prior Therapy

All prior drug therapies for PsA (arthritis and psoriasis), since initial diagnosis, must be recorded in the eCRF along with the dates of first and last dose, maximum dosage taken, route of administration and reason for discontinuation, if known. Additionally, the investigator will record response to DMARDs (e.g., no response, inadequate response, loss of response), intolerance to DMARD and/or contraindication for DMARDs.

5.2.3.2 Permitted Background Therapy

In Period 1, if subjects are on background DMARDs they should continue on stable treatment of up to 2 non-biologic DMARDs (DMARDs should have been started ≥ 12 weeks prior to the Baseline visit and without dosing or administration changes ≥ 4 weeks prior to the Baseline visit). The following non-biologic DMARDs are allowed as background therapy during the study: MTX (≤ 25 mg/week), SSZ (≤ 3000 mg/day), leflunomide (LEF) (≤ 20 mg/day), apremilast (≤ 60 mg/day), HCQ (≤ 400 mg/day), bucillamine (≤ 300 mg/day) and iguratimod (≤ 50 mg/day). In addition, for all subjects taking MTX, subjects should take a dietary supplement of oral folic acid (or equivalent, such as folinic acid) throughout study participation. Folic acid dosing and timing of regimen should be followed according to Investigator's instructions. No other DMARDs are permitted during the first 36 weeks of study participation in Period 1. At any time, the background DMARD dose may be decreased for safety reasons. AbbVie will not provide background DMARDs or folic acid.

In the first 36 weeks of study participation in Period 1, subjects should also continue on their stable doses of NSAIDs, acetaminophen/paracetamol, low-potency opiates (tramadol or combination of acetaminophen with codeine or hydrocodone), oral corticosteroids (equivalent to prednisone ≤ 10 mg/day). If taking any of the above on a scheduled basis, they should continue to take them as they did at study entry with no change in dose or frequency, including on study visit days. If not taking any of the above at baseline, these

[figure not shown]

should not be initiated except where permitted by protocol (specific time period or protocol-defined rescue). If taking any of the above at baseline on an as-needed basis (PRN), they should continue to use them for the same reason and same dose each time but they should not be taken within the 24 hours prior to any study visit to avoid bias in outcome measurements. In the event of tolerability (or other safety) issues, these medications may be decreased, or discontinued with substitution of another permitted medication from that class. PRN use of inhaled corticosteroids is permitted at any time.

In Periods 1 and 2, starting at Week 36 (after Week 36 assessments have been performed) and thereafter, 1 intra-articular, trigger point or tender point, intra-bursa, or intra-tendon sheath injections of corticosteroids, dosage and frequency per standard of care, is allowed every 12 weeks. However, corticosteroid injections should be avoided within 21 days prior to the next scheduled study visit to avoid confounding effects of systemic absorption of intra-articular, trigger point or tender point, intra-bursa, and intra-tendon sheath corticosteroids.

In addition, at Week 36 (after Week 36 assessments have been performed) and thereafter, initiation of or change in corticosteroids, NSAIDs, acetaminophen/paracetamol, low-potency opiates (tramadol or combination of acetaminophen with codeine or hydrocodone) or adding or changing doses of non-biologic DMARDs (MTX, LEF, SSZ, apremilast, HCQ, bucillamine or iguratimod) is allowed as per local label. Concomitant use of up to 2 non-biologic DMARDs (MTX, LEF, SSZ, apremilast, HCQ, bucillamine or iguratimod) except the combination of MTX and LEF is permitted. Doses of non-biologic DMARDs and oral corticosteroids may not exceed maximums defined above and in inclusion criteria (Section 5.2.1).

After the Week 16 visit has been completed, a subject who qualifies for rescue therapy will be permitted to add or modify doses of non-biologic DMARDs, NSAIDs, acetaminophen/paracetamol, low potency opioid medications (tramadol or combination of acetaminophen and codeine or, hydrocodone), oral corticosteroids, and/or receive 1 intra-articular, trigger point or tender point, intra-bursa, or intra-tendon sheath corticosteroid injection for 1 peripheral joint, 1 trigger point, 1 tender point, 1 bursa, or 1 enthesis as

described in Section 5.2.3.4 (Rescue Therapy). Corticosteroid injections should be avoided within 21 days prior to the next scheduled study visit to avoid confounding effects of systemic absorption of corticosteroids.

In Period 1 and Period 2 permitted topical treatments for Psoriasis (PsO) include:

- Non-medicated shampoos
- Bland (without beta or alpha hydroxy acids, urea or salicylic acid) emollients
- Low potency (Class VI or VII) topical corticosteroids on the palms, soles, face, inframammary area and groin only.

Starting at Week 16 (after Week 16 assessments have been performed) and thereafter, subjects may use any therapy for PsO per investigator judgment, with the exception of non-biologic DMARDs which may not be initiated or modified at Week 16 unless non-responder criteria are met as detailed in Section 5.2.3.4 Rescue Therapy. At Week 36 and thereafter, initiation of or change in dose of non-biologic DMARDs is permitted, as described above.

[figure not shown]
5.2.3.3 Prohibited Therapy

Non-Biologic DMARDs

Prior exposure to or concomitant use of JAK/TYK2 inhibitors (including but not limited to commercial upadacitinib [Rinvoq®], ruxolitinib [Jakafi®, Opzelura®], tofacitinib [Xeljanz®], baricitinib [Olumiant®], peficitinib [Smyraf®], abrocitinib [Cibinqo®], filgotinib [Jyseleca®], fedratinib [Inrebic®], and deucravacitinib [Sotyktu®]) is not allowed.

Use of MTX in combination with LEF is NOT allowed.

Concomitant therapy with > 2 non-biologic DMARDs or therapy with DMARDs other than MTX (≤ 25 mg/week), SSZ (≤ 3000 mg/day), leflunomide (LEF) (≤ 20 mg/day), apremilast (≤ 60 mg/day), HCQ (≤ 400 mg/day), bucillamine (≤ 300 mg/day) and

iguratimod (≤ 50 mg/day). Subjects must have discontinued all other non-biologic DMARDs prior to Baseline Visit as specified in Inclusion Criterion 7, Section 5.2.1.

Corticosteroids

Intravenous (IV), intramuscular (IM) and epidural corticosteroids are NOT allowed.

Biologic Therapies

All prior and concomitant biologic therapies with immunosuppression potential, and biosimilar versions of biologic drugs for treatment of PsA are prohibited during the study (Period 1 and Period 2). Examples of biologic therapies include but are not limited to the following:

- Humira® (adalimumab)
- Orencia® (abatacept)
- Kineret® (anakinra)
- Saphnelo® (anifrolumab)
- Benlysta® (belimumab)
- Cimzia[®] (certolizumab pegol)
- Prolia® (denosumab)
- Dupixent® (dupilumab)
- Raptiva® (efalizumab)
- Enbrel[®] (etanercept)
- Simponi[®] (golimumab)
- guselkumab
- Remicade® (infliximab)
- Taltz[®] (ixekizumab)
- lebrikizumab
- Tysabri[®] (natalizumab)
- nemolizumab

ABT-494
M15-572 Protocol Amendment 8
EudraCT 2016-004130-24

- Rituxan® (rituximab)
- Skyrizi[®] (risankizumab)
- Cosentyx® (secukinumab)
- Actemra® (tocilizumab)
- tralokinumab
- Stelara® (ustekinumab)
- Entyvio® (vedolizumab)

Strong CYP3A Inhibitors or Inducers

Systemic use of known strong CYP3A inhibitors or strong CYP3A inducers is excluded from the Screening Visit through the end of the study. This includes over-the-counter or prescription medicines, vitamins, herbal supplements, and/or traditional medicines. The most commonly strong CYP3A inhibitors and inducers are listed in Table 1.

[figure not shown]

Table 1. Examples of Commonly Used Strong CYP3A Inhibitors and Inducers

[figure not shown]
Strong CYP3A Inhibitors	Strong CYP3A Inducers	
Boceprevir	Apalutamide	
Ceritinib	Carbamazepine	
Cobicstat	Enzalutamide	
Clarithromycin	Ivosidenib	
Conivaptan	Lumacaftor	
Grapefruit (fruit or juice)	Mitotane	
Idelalisib	Phenytoin	
Itraconazole	Rifampin (Rifampicin)	
Ketoconazole	Rifapentine	
Mibefradil	St. John's Wort	
Nefazodone		
Nelfinavir		
Posaconazole		
Ritonavir (alone or in combination with danoprevir, elvitegravir, indinavir, lopinavir, nirmatrelvir, paritaprevir, saquinavir, telaprevir, tipranavir, ombitasvir and/or dasabuvir)		
Telithromycin		
Troleandomycin		
Voriconazole		

Cannabis

Use of inhaled medicinal and recreational marijuana is prohibited during the study and subjects must have discontinued use at least 2 weeks prior to Baseline.

Opiates

Opiates, with the exception of tramadol or combination of acetaminophen and codeine or hydrocodone, are not permitted during the study, and subjects must have discontinued

prohibited opiates at least 1 week prior to the first dose of study drug, including (but not limited to):

- buprenorphine
- codeine
- fentanyl
- hydrocodone
- hydromorphone
- levorphanol
- meperidine
- methadone
- morphine
- oxycodone
- oxymorphone
- propoxyphene

[figure not shown]
Low potency opioid medications limited to tramadol or combination of acetaminophen and codeine or hydrocodone are permitted during the study.

Traditional Chinese Medications

Oral or parenteral Traditional Chinese Medicine is not permitted during the study, and subjects must have discontinued Traditional Chinese Medicines at least 4 weeks prior to the first dose of study drug. Subjects may not use oral or parenteral Traditional Chinese Medicines during the study including for treatment of AEs.

Investigational Drugs

Subjects who have been treated with any investigational drug within 30 days or five half-lives of the drug (whichever is longer) prior to the first dose of study drug are excluded from participation in this study. Investigational drugs are also prohibited during the study.

Vaccines

Although not mandated by the protocol, vaccines recommended by local guidelines should be considered. If the subject and investigator choose to administer live vaccines with replicating potential, these vaccinations must be completed at least 4 weeks (8 weeks in Japan) before first dose of study drug. Live vaccines with replicating potential are prohibited during the study participation including at least 30 days after the last dose of study drug.

[figure not shown]
Examples of live vaccines with replicating potential include, but are not limited to, the following:

- Monovalent live attenuated influenza A (H1N1) (intranasal);
- Seasonal trivalent live attenuated influenza (intranasal);
- Herpes zoster (Zostavax[®], live attenuated);
- Rotavirus;
- Varicella (chicken pox);
- Measles-mumps-rubella or measles mumps rubella varicella;
- Oral polio vaccine;
- Smallpox or monkeypox vaccine capable of replicating;
- Yellow fever;
- Bacille Calmette-Guérin (BCG);
- Typhoid (oral).

Examples of common vaccines that are inactivated, toxoid or biosynthetic, include but are not limited to: injectable influenza vaccine, pneumococcal and, pertussis (Tdap) vaccines.

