5.5 Treatments

5.5.1 Treatments Administered

There are two active study drugs in this study. The first is daily upadacitinib and the second is ADA eow.

Upadacitinib (or matching placebo) will be taken orally once daily, beginning on Day 1 (Baseline), and should be taken at approximately the same time each day. The study drug can be taken with or without food. Subjects will continue their stable background non-biologic DMARD therapy. AbbVie will not supply background DMARDs.

ADA (or matching placebo) will be provided as a subcutaneous injection solution in 1 mL pre-filled syringes containing ADA 40 mg/0.8 mL (or matching placebo). ADA (or matching placebo) will be subcutaneously administered eow at approximately the same time of day.

Subjects taking MTX as background therapy should take a dietary supplement of oral folic acid beginning on Day 1 (Baseline) throughout study participation. Folic acid dosing and timing of regimen should be followed according to the Investigator's instructions. AbbVie will not supply folic acid (or equivalent, such as folinic acid).

Subjects will receive both oral study drug QD (either upadacitinib 15 mg, upadacitinib 30 mg, or matching placebo) and subcutaneous study drug eow (either ADA 40 mg or matching placebo). When the last subject completes the Week 56 visit, study drug assignment in both periods will be unblinded to the sites, and subjects will be dispensed study drug in an open-label fashion until the completion of Period 2.

Upon approval of protocol amendment 7, subjects receiving upadacitinib 30 mg QD will be switched to upadacitinib 15 mg QD at their next scheduled study visit.

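### Protocol 5.2.3.3 sets one 30-day live-vaccine floor for both study drugs, while exclusion 9 and Section 5.2.3 set 70 days after the last injection

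*Protocol*

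**What the plan says.** Three places in the protocol body set a live-vaccine interval after dosing.

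- **Section 5.2.3.3, Prohibited Therapy (Vaccines).** This is the outright on-study ban: "Live vaccines with replicating potential are prohibited during the study participation including at least 30 days after the last dose of study drug". One interval applies to study drug as a whole.
- **Section 5.2.2, exclusion criterion 9.** A subject is excluded if a live vaccine is expected to be needed during the study or for a set time afterwards. Oral drug has its own interval, and the criterion then adds "and including at least 70 days after the last dose of subcutaneous study drug".
- **Section 5.2.3, Prior and Concomitant Therapy (Vaccines).** The live zoster vaccine, if not given before the study, should be "administered at least 30 days after last dose of oral study drug, or at least 70 days after last dose of subcutaneous study drug".

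Two further passages tie these together. Section 5.5.1 states: "There are two active study drugs in this study", namely daily upadacitinib and every-other-week adalimumab, so the term study drug covers both. Section 5.2.3 also sends the reader onward: "See Section 5.2.3.3 for a list of commonly used live vaccines". The list found there includes live zoster, "Herpes zoster (Zostavax", alongside others such as "Measles-mumps-rubella or measles mumps rubella varicella".

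**The concern.** A site reading 5.2.3.3 alone finds 30 days after the last dose of either drug. A site reading exclusion 9 or Section 5.2.3 finds 70 days after an injection. For live zoster vaccine the two intervals apply to the same product, because Section 5.2.3 points to the list in 5.2.3.3 and zoster is on it.

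The shorter figure sits in the only outright on-study prohibition. Exclusion 9 is an entry criterion about expected need, and the Section 5.2.3 text is a recommendation for one vaccine. SAP 11.1 (version dated July 2021) records Period 1 reporting as complete, so remaining subjects are well past entry and 5.2.3.3 is the section a site would naturally consult. What is at stake is the advice given to someone who has recently stopped adalimumab. No trial result is at stake.

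**Working it through.** The interval is a stated rule and not a derived quantity, so the check is a comparison of texts and one subtraction.

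**1. Stated floors after the last dose**

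| Source | After oral drug | After injected drug |
|---|---|---|
| 5.2.3.3 | 30 days (routes not separated) | 30 days (routes not separated) |
| 5.2.3, zoster vaccine | 30 days | 70 days |
| Exclusion 9 | own interval | 70 days |

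**2. Size of the difference.** After injected drug: 70 - 30 = 40 days. Between 5.2.3.3 and 5.2.3 the oral floor is the same: 30 - 30 = 0 days. The figure in 5.2.3.3 is therefore the oral interval applied to both drugs.

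**3. Is a shorter interval after adalimumab intended?** No text gives a reason for one. Elsewhere the documents separate the routes at 30 and 70 days: adverse event collection (Protocol 6.1.4), follow-up contacts (Protocol 5.1, Follow-Up Period) and the treatment-emergent definition (SAP 10.2). Exclusion 9 is built much like the 5.2.3.3 sentence, with study participation followed by a minimum time after dosing, and it still adds the 70 days for injected drug.

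**4. Who is actually left with the 30-day floor?** The 5.2.3.3 ban has two parts: the time in the study, and a minimum after the last dose. Taking adalimumab subjects by how they leave treatment:

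- *Completers.* Section 5.1.1 has them finish the study with the 70-day call, and Section 13.0 counts a subject as complete only after the Week 260 visit and the safety follow-up. The ban therefore runs to about day 70.
- *Completers who start commercial adalimumab.* The follow-up contact is waived, but they continue the same drug outside the study.
- *Subjects who stop drug but stay in the study.* Section 5.4.1 keeps them on the regular visit schedule. They are still taking part and still under the ban, whether or not the optional 70-day call is made.
- *Subjects who withdraw from the study.* Participation ends, so only the minimum after the last dose applies, and 5.2.3.3 puts it at 30 days. Section 5.1 and Appendix C footnote b provide a 70-day call for them, but Section 5.1 gives its purpose as adverse event status and attaches no vaccine restriction.

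Only the last group falls in the gap, from about day 31 to day 69 after the last injection.

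**The case against.** The strongest reply is that nothing conflicts. A floor worded as at least 30 days, inside a ban that covers the whole of participation, does not authorise vaccination on day 31. Exclusion 9 covers any live vaccine, Section 5.2.3 gives 70 days for zoster and directs questions on concomitant therapy to the sponsor's medical director, and a subject who waits 70 days satisfies every passage. It can be added that a prohibited-therapy rule has little hold on someone who has withdrawn, and that Section 5.4.1 leaves treatment after study drug to the investigator's clinical judgment.

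Much of this stands. A reader might infer that any adalimumab subject may receive a live vaccine from day 31. The documents do not support that, because participation keeps the ban in place for completers and for those who stop drug but remain. A reader might also infer that the protocol positively permits vaccination at day 31, and it does not say so. What the reply does not remove is the withdrawal case. There the only on-study prohibition names 30 days, exclusion 9 speaks to entry, and Section 5.2.3 advises on zoster alone.

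Timing also weakens the practical force. SAP Appendix F puts the Week 24 database lock in January 2020, after the last Week 24 visit. Week 260 is 260 - 24 = 236 weeks later, which gives about August 2024 at the latest for the last scheduled Week 260 visit. The Amendment 8 synopsis is dated 20 December 2023. This is inference from dates, since the documents give no last-subject date, but few adalimumab subjects may remain for a correction to reach.

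**Conclusion.** The 5.2.3.3 sentence is wrong as written, and the fault is minor. It gives a post-injection floor 40 days shorter than the 70 days stated in exclusion 9 and Section 5.2.3, without a reason. The practical gap is limited to adalimumab subjects who withdraw from the study. Their number is not in the documents and is probably small.

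The conclusion rests on two readings. The first is that study drug in 5.2.3.3 includes adalimumab, which Section 5.5.1 supports. The second is that participation extends to the 70-day call for adalimumab completers, which Sections 5.1.1 and 13.0 support although 5.2.3.3 does not define the term. If participation were taken to end at the Week 260 visit, completers would fall in the gap as well, but that reading goes against Section 13.0.

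No endpoint, estimand, power figure or analysis is affected, and it would be a mistake to infer that any efficacy or safety result is in doubt. The point concerns the subcutaneous interval only; the oral intervals are outside it.

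**What to change.** In Protocol 5.2.3.3, replace the single interval with two. Live vaccines with replicating potential would be prohibited while the subject is in the study, and for at least 30 days after the final oral dose and at least 70 days after the final injection. This matches Section 5.2.3 and agrees with exclusion 9 on the injected drug.

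The cost is one sentence, carried in the next amendment or administrative change. No statistical text, data collection or analysis needs to change.
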